**Table 9-1 Candidate dose-response models in consideration**

#	Candidate models for qd regimen	Candidate models for bid regimen
1	$E_{max}$ model: $ED_{50} = 5$ mg	$E_{max}$ model: $ED_{50} = 5$ mg
2	$E_{max}$ model: $ED_{50} = 50$ mg	$E_{max}$ model: $ED_{50} = 50$ mg
3	Sigmoid $E_{max}$ : $ED_{50} = 75$ mg, $H = 3.5$	Sigmoid $E_{max}$ : $ED_{50} = 75$ mg, $H = 3.2$
4	Sigmoid $E_{max}$ : $ED_{50} = 25$ mg, $H = 0.7$	Linear log-dose: null, $c = 0.8$
5	$\beta$ -model: $\alpha = 0.8$ , $\beta = 0.2$ , scale = 180	Linear
6	Exponential: $\lambda = 125$	Quadratic: $\delta = -0.007$

**Figure 9-1 Dose-response curve of candidate models (left panel: qd regimen)**

The analysis to derive the test statistics is based on an analysis of covariance (ANCOVA) model with the percent change in body weight from BL to Week 24 as a response variable, treatment (placebo and all LIK066 doses from each regimen), stratum indicator (dysglycemic/normoglycemic/T2DM) and pooled center/region as factors and BL weight as a covariate. As needed, centers will be pooled according to country and region for the purpose of analysis.

The response variable of percent change in body weight from BL to Week 24 used in the above ANCOVA is from an imputed dataset, where the missing Week 24 weight is imputed using the multiple imputation method as described in [Section 9.4.3](#). In order to account for the imputation uncertainty, this ANCOVA model will be repeated for each imputed dataset, which results in a set of least squares (LS) mean estimates for all dose groups for the two regimens and the related covariance matrices. Rubin's rule will be used to combine the multiple sets of LS mean estimates and the related covariance matrices to a single set of LS mean estimates of percent changes of body weight at Week 24 for all dose groups and the related covariance matrix.

The optimal contrasts derived from the candidate model sets will be applied to the combined estimated dose means and covariance matrix to obtain the t statistics for each candidate model in the two regimens and the common critical value  $C_{0.025}$ .  $C_{0.025}$  is the common critical value derived from the reference multivariate t-distribution with the  $12 \times 12$  correlation matrix induced by testing the candidate dose response models with respect to comparing all candidate models in both dosing regimens to the common placebo group.

The intersection hypotheses  $H_{01}$  and  $H_{02}$  will be rejected and the statistical significance of dose-response in body weight reduction is established if the  $\max(t_1, t_2, t_3, \dots, t_{11}, t_{12}) \geq C_{0.025}$ . In other words, the intersecting null hypothesis requires the rejection of either  $H_{01}$  or  $H_{02}$ .

[figure not shown]
### **Model averaging to obtain the dose responses for qd and bid dosing regimens**

The response data in each imputed data set, including relevant covariates, will be used to fit the models in the candidate set within each dosing regimen. The estimated dose-response in each dosing regimen will be derived by using model averaging methods on a subset of candidate models, for which the associated contrast tests are statistically significant. If there are more than three candidate models that are statistically significant, then only the top three candidate models with the largest test statistics will be selected. Model averaging will be carried out for each imputed data set, and the resulting mean efficacy estimates and confidence intervals will be derived using the combination variance that accounts for the uncertainty of the imputed data using Rubin's combination rules. Comparisons between LIK066 doses and placebo in each dosing regimen will be simultaneously derived for the model averaged estimates together with confidence intervals reflecting the imputation procedure applied.

Target dose selection will be based on the model averaged dose response estimates of mean weight lowering efficacy of LIK066 over the dose range studied in the Phase 2B study.

#### **9.4.3 Handling of missing values/censoring/discontinuations**

Missing data for the primary endpoint will be imputed using a multiple imputation approach that assumes that the missingness mechanism can be retrieved from observed data (missing at random; MAR). The imputation model will include the longitudinal sequence of body weight data collected at each visit up to and including Week 24 visit and BL covariates (eg randomization stratification factor, FPG, age, gender, race), imputing missing visit observations for each dose group separately.

The full detailed information about the multiple imputation algorithms will be specified in a separate statistical analysis plan.

#### **9.4.4 Supportive analyses**

As a sensitivity analysis, the dose-response modeling as described in [Section 9.4.2](#) will be conducted in the PPS as well.

Results based on the single best dose response model fit will also be reported.

Summary statistics for body weight will be presented by visit by treatment for observed and imputed values. The summary statistics n, mean, standard deviation (SD), median, minimum, maximum, Q1 and Q3 will be presented for the BL values and similarly for absolute values at and changes from BL to the post-BL visits. Figures will be produced to visually show the raw and the imputed mean changes by visit over 24 weeks of Epoch 3 for each treatment group, for all subjects and by strata separately.

### **9.5 Analysis of secondary variables**

#### **9.5.1 Efficacy variables**

##### **9.5.1.1 Week 24 analysis**

###### **Variables**

- Responder rates based on percent decrease in body weight from BL at Week 24  $\geq 5\%$ , or  $\geq 10\%$ .
- Dose-response relationship in normoglycemic subjects, dysglycemic subjects and subjects with T2DM after 24 weeks of treatment.
- Change from BL at Week 24 in waist circumference.
- Change from BL at Week 24 in HbA1c.
- Change from BL at Week 24 in FPG.
- Change from BL at Week 24 in SBP and DBP.
- Changes from BL at Week 24 in the fasting lipid profile (TG, total cholesterol, high density lipoprotein (HDL) cholesterol, low density lipoprotein (LDL) cholesterol, lipoproteins, calculated very low density lipoprotein (VLDL) cholesterol and non-HDL cholesterol) and hsCRP.
- Change from BL at Week 24 in 24-h UGE.

###### **Analysis method: responder analysis**

For the responder analysis, a logistic regression model will be performed using the percent decrease in body weight from BL at Week 24  $\geq 5\%$  or  $\geq 10\%$  (yes/no) as a response variable, treatment, glycemic stratification factor and pooled center as fixed factors and BL body weight as a covariate, respectively. The Week 24 missing values will be imputed using the multiple imputation method as described in [Section 9.4.3](#). In order to account for the

imputation uncertainty, this logistic regression model will be repeated for each imputed dataset, which results in a set of estimated odds ratio and its 95 % confidence interval of an LIK066 dose *vs* placebo for all dose groups for the two regimens. Rubin's rule will be used to combine the multiple sets of odds ratios and 95 % confidence intervals to a single set of odds ratio and its 95 % confidence interval of an LIK066 dose *vs* placebo. Similar analysis by glycemic status stratification factor will be performed to assess the responder across each of the subgroups (normoglycemic subjects, dysglycemic subjects and subjects with T2DM).

In addition, subjects meeting the predefined response criteria (percent decrease in body weight from BL at Week 24  $\geq$  5 % or  $\geq$  10 %) will be summarized by treatment for all subjects and by glycemic stratification factor. A Cochran-Mantel-Haenszel-test will be performed to compare each qd or bid dose to the common placebo.

### **Analysis method: dose-response relationship by glycemic stratification factor**

For the dose-response relationship in normoglycemic subjects, dysglycemic subjects and subjects with T2DM, the dose-response modeling with the same candidate model sets for the primary variable as described in [Section 9.4.2](#) will be performed on percent change of body weight from BL at Week 24 for these three subsets of subjects separately.

### **Analysis for other secondary endpoints**

For changes from BL at Week 24 in HbA1c, FPG, SBP, DBP, waist circumference and 24-h UGE, a repeated measure ANCOVA model with treatment, visit, and treatment by visit interaction as fixed-effect factors and BL as a covariate, and a common unstructured covariance matrix among visits between treatments will be performed separately for each variable. The adjusted mean changes at Week 24 within each treatment, the differences in mean changes at Week 24 between the LIK066 and placebo treatments, and their 95 % confidence intervals obtained from the above model will be presented. The analysis is based on likelihood method with an assumption of MAR for missing data.

In addition, a repeated measure ANCOVA model with treatment, visit, stratification factor (normoglycemic, dysglycemic, T2DM) and treatment by visit, treatment by stratification factor and treatment by visit by stratification factor interactions as fixed-effect factors and BL as a covariate, and a common unstructured covariance matrix among visits between treatments will be performed for the primary and secondary efficacy variables, respectively. The adjusted mean changes at Week 24 within each treatment, the differences in mean changes at Week 24 between the LIK066 and placebo treatments for each stratum, and their 95 % confidence intervals obtained from the above models will be presented by strata for each efficacy endpoint.

Similar repeated measure ANCOVA models will be performed for percent changes of lipid parameters and hsCRP from BL at Week 24.

Summaries of absolute values and change from BL by treatment group and visit will be presented for all secondary efficacy variables for all subjects and by strata. Figures will be produced to visually show the raw mean changes by visit over 24 weeks of Epoch 3 for each treatment group, for overall and by strata separately.

All analyses on secondary variables will be performed in the FAS.

### **9.5.1.2 End of study analysis**

A repeated measure ANCOVA model with treatment, visit, the stratification factor, pooled center or region, and treatment by visit interaction as fixed-effect factors and BL as a covariate, and a common unstructured covariance matrix among visits between treatment will be performed separately for the changes from Week 24 to study end in each efficacy variable (body weight, FPG, HbA1c, SBP, DBP, lipid parameters, hsCRP, 24-h UGE and waist circumference). The adjusted mean changes from Week 24 to Week 48 within each treatment, the differences in mean changes from Week 24 to Week 48 between the LIK066 and placebo treatments, and their 95 % confidence intervals obtained from the above models will be presented. The analysis is based on likelihood method with an assumption of MAR for missing data.

A similar repeated measure ANCOVA model with additional glycemic stratification factor by treatment interaction and treatment by visit by stratification factor interaction terms will be performed to assess the body weight change from Week 24 to study end across each of the subgroups (normoglycemic subjects, dysglycemic subjects and subjects with T2DM). The p-value for the interaction of treatment by stratification factor at Week 24 will be calculated from this model as well.

Note that for lipid parameters, the percent changes (instead of absolute change) from Week 24 to study end will be used as a response variable in the above repeated measure ANCOVA model.

Summaries of absolute values and changes (and/or percent changes for body weight and lipid parameters) from Week 24 by treatment group and visit will be presented for all efficacy variables, for all subjects and by stratification strata, respectively. Changes from BL will be similarly summarized as well. Figures will be produced to visually show the raw mean changes by visit over entire study period of 48 weeks for each treatment group.

All analyses will be performed in subjects in the FAS who enter Epoch 4.

### **9.5.2 Safety variables**

#### **9.5.2.1 Week 24 analysis**

All safety analyses will be performed in the SAF.

#### **AEs**

Treatment emergent AEs will be summarized. A treatment-emergent AE is defined as any AE that develops after initiation of the study treatments or any event already present that worsens following exposure to the study treatment. The number and percentage of subjects having AEs will be presented by treatment group and different hierarchy levels of the MedDRA coding dictionary. Summaries will also be presented by greatest severity, for AEs suspected to be related to study drug, serious AEs, AEs leading to discontinuation, to dosage adjustment, to death and other significant AEs. The hypoglycemic events will be similarly summarized. Further information related to hypoglycemic events (eg if third party assistance required, was medical assistance received, etc.) may be provided as well.

AEs related to identified and potential risks as specified in the development safety profiling plan (DSPP) will be summarized and presented separately.

The frequencies and percentages of the adjudication confirmed ketoacidosis events will be provided by treatment.

In addition, for selected AEs including hypotension, hypoglycemia, hyperkalemia, diarrhea, and genital and UTI, a by-stratification factor of BL glycemic status subgroup analysis will be provided.

### **Laboratory data, vital signs, ECG and bone markers**

Descriptive summary statistics including for the change from BL to each study visit up to and including Week 24 visit will be presented by treatment group for each laboratory parameter, as well as for the maximum change from BL. In addition, shift tables will be provided for all parameters with available ranges to compare a subject's BL laboratory evaluation relative to the most extreme post-BL value. For the shift tables, normal ranges as well as specifically defined clinically notable/abnormality limits, if available – will be used.

The vital sign and ECG data collected during Epoch 3 will be descriptively summarized by treatment as appropriate.

The change from BL in the 24-h urinary calcium and phosphorus excretion will be descriptively summarized by treatment and visit for a subset of subjects participating in the PK analysis.

#### **9.5.2.2 End of study analysis**

All safety analyses will be performed for subjects in the SAF who enter Epoch 4.

### **AEs**

The number and percentage of subjects having AEs, SAEs, AEs leading to study medication permanent discontinuation and other significant AEs occurred during Epoch 4 will be summarized and presented by treatment. Similar summaries will be provided for events occurred during the overall 48 weeks of Epoch 3 plus Epoch 4.

The AEs of interest, including those related to potential/identified risks as specified in the DSPP, will be summarized as appropriate separately.

### **Laboratory data, vital signs and ECG**

Descriptive summary statistics including for the change from Week 24 to each post-Week 24 study visit during Epoch 4 will be presented by treatment group for each parameter, as well as for the maximum change from BL. In addition, shift tables will be provided for all parameters with available ranges to compare a subject's Week 24 laboratory evaluation relative to the most extreme post-Week 24 value.

The change from Week 24 in the 24-h urinary calcium and phosphorus excretion will be descriptively summarized by treatment and visit (for post-Week 24 visits only) for a subset of subjects participating in the PK analysis.

### **9.5.3 Resource utilization**

Not applicable.

### **9.5.4 PK**

The following PK parameters will be determined using the actual recorded sampling times and non-compartmental method(s) with Phoenix WinNonlin (Version 6.2 or higher): maximum concentration observed (Cmax), maximum time (Tmax), last non-zero concentration area under the curve (AUClast), AUC0-t. Additional PK parameters may be calculated as appropriate. The linear trapezoidal rule will be used for AUC calculation.

Descriptive summary statistics will be provided by treatment and visit/sampling time point. Summary statistics will include mean (arithmetic and geometric), SD, CV (arithmetic and geometric), median, minimum and maximum. An exception to this is Tmax where median, minimum and maximum will be presented.

Concentrations below the lower limit of quantification (LLOQ) will be treated as zero in summary statistics and for PK parameter calculations. A geometric mean will not be reported if the dataset includes zero values.

Individual LIK066 plasma concentration data will be listed by treatment, subject, and visit/sampling time point. PK parameters will also be listed by treatment and subject.

### **9.5.5 DNA**

Not applicable.

[figure not shown]
[figure not shown]
### **9.5.6 Biomarkers**

[figure not shown]
#### **Week 24 analysis**

Summaries of absolute values and change from BL in each of the bone, renal and inflammatory biomarkers by treatment group and visit will be presented using statistics: n, mean, SD, median, minimum, maximum, Q1, Q3, geometric mean and coefficient of variation. Figures will be produced to visually show the mean values by visit over 24 weeks of treatment in Epoch 3 for each treatment group.

#### **End of study analysis**

The absolute values and change from Week 24 in each of the bone, renal and inflammatory biomarkers will be similarly summarized and depicted as for the Week 24 analysis.

## **9.7      Interim analyses**

Not applicable.

## 9.8 Sample size calculation

The study planned to randomize approximately 432 subjects in total, allocated in the ratio of 1:1:1:1:1:2:1:1:1:2 to the following ten Epoch 3/Epoch 4 treatment groups:

1. placebo/placebo
2. placebo/LIK066 25 mg qd
3. LIK066 2.5 mg qd/25 mg qd
4. LIK066 10 mg qd/25 mg qd
5. LIK066 50 mg qd/25 mg qd
6. LIK066 150 mg qd/25 mg qd
7. LIK066 2.5 mg bid/35 mg qd
8. LIK066 5 mg bid/35 mg qd
9. LIK066 25 mg bid/35 mg qd
10. LIK066 50 mg bid/35 mg qd

This randomization scheme implies that the Epoch 3 treatment and Epoch 4 treatment for a specific subject is determined simultaneously at randomization visit. The randomization will be stratified by subjects' glycemic status at screening: normoglycemic, dysglycemic and T2DM (see [Section 3.1.2](#)).

As the dose-response assessment is conducted in qd and bid regimens separately (while an overall family-wise type I error is controlled at a one-sided significance level of 2.5 %), power calculation was done for testing dose-response signal by regimen as well. [Table 9-2](#) summarizes the average power and the lowest power across the candidate dose response shapes in [Figure 9-1](#) by regimen, under different scenarios with the assumptions on effect size of body weight loss (percent change from BL) for the dose of maximum effect, and the related standard deviations.

Note that a dose-response signal is detected (ie the primary objective is met) as long as either of the dose-response signals for the two regimens is detected. Therefore, the overall study power is at least the maximum of the powers between two regimens for each scenario considered.

It was assumed that the effect of losses to follow-up is equivalent to effectively having 15 % fewer subjects than randomized, even if the multiple imputation approach used to handle missing values should be able to recover some information for such subjects.

**Table 9-2 Power for detecting a significant dose response signal\***

Dose regimen	Effect size for best dose	SD	Average power**	Minimum power†
qd	5 %	5.5 %	99.99 %	99.98 %
	5 %	6.5 %	99.71 %	99.57 %
	6 %	5.5 %	99.99 %	99.99 %
	6 %	6.5 %	99.99 %	99.98 %

Dose regimen	Effect size for best dose	SD	Average power**	Minimum power †
bid	5 %	5.5 %	99.16 %	95.84 %
	5 %	6.5 %	96.50 %	86.79 %
	6 %	5.5 %	99.90 %	99.43 %
	6 %	6.5 %	99.28 %	96.36 %

\* Assumes 432 subjects in LIK066 and placebo arms with effective sample size of 367 subjects due to an effect of missing data equivalent to 15 % fewer subjects. Calculations were performed using the DoseFinding package in R.

† Power for a significant dose-response contrast test across all scenarios within each regimen in [Table 9-1](#). The candidate model #5 in bid regimen has the lowest power.

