### Test of the dose response signal

The null hypothesis of a flat dose-response relationship for the percentage reduction in body weight compared to placebo will be tested at a one-sided significance level of 2.5 % against the alternative hypothesis of a dose-response relationship leading to a significant decrease in percent body weight.

Hence, the following null and alternative hypotheses will be tested:

- $H_{01}$ : there is no dose-response relationship for LIK066 given qd (ie the dose response relationship is flat).
- $H_{11}$ : there is a dose-response relationship for LIK066 given qd (ie as dose increases, the percent weight decreases).
- $H_{02}$ : there is no dose response relationship for LIK066 given bid (ie the dose response relationship is flat).
- $H_{12}$ : there is a dose-response relationship for LIK066 given bid (ie as dose increases, the percent weight decreases).

Given that we suspect the dose-response may behave differently between qd and bid regimens based on the data we have seen from the proof-of-concept study LIK066X2201, we define separate sets of the dose-response candidate models for each dosing regimen. In order to preserve the family-wise error rate at one-sided significance level of 2.5 %, the optimal contrasts derived from the model candidate set for each dosing regimen will be individually

[figure not shown]
compared to the critical value derived using a multiplicity adjustment accounts for all tests of comparing LIK066 doses to placebo across regimens simultaneously as described above. The rejection of the null hypothesis for each dosing regimen will be achieved using the maximum test statistic in each dosing regimen from each estimated contrast test in the candidate set.

The candidate models generating the contrast weights are described in [Table 9-1](#) and depicted in [Figure 9-1](#), with the doses used to define parameters of interest being defined as total daily dose.

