2.14 Interim analysis

Not applicable.

3 Sample size calculation

The study planned to randomize approximately 432 subjects in total, allocated in the ratio of 1:1:1:1:1:2:1:1:1:2 to the following 10 Epoch 3/Epoch 4 treatment groups:

1. placebo/placebo
2. placebo/LIK066 25 mg qd
3. LIK066 2.5 mg qd/25 mg qd
4. LIK066 10 mg qd/25 mg qd
5. LIK066 50 mg qd/25 mg qd
6. LIK066 150 mg qd/25 mg qd
7. LIK066 2.5 mg bid/35 mg qd
8. LIK066 5 mg bid/35 mg qd
9. LIK066 25 mg bid/35 mg qd
10. LIK066 50 mg bid/35 mg qd

This randomization scheme implies that the Epoch 3 treatment and Epoch 4 treatment for a specific subject is determined simultaneously at randomization visit. The randomization will be stratified by subjects' glycemic status at screening: normoglycemic, dysglycemic and T2DM.

As the dose-response assessment is conducted in qd and bid regimens separately (while an overall family-wise type I error is controlled at a one-sided significance level of 2.5 %), power calculation was done for testing dose-response signal by regimen as well. Table 3-1 summarizes the average power and the lowest power across the candidate dose response shapes in Figure 2-1 by regimen, under different scenarios with the assumptions on effect size of body weight loss (percent change from BL) for the dose of maximum effect, and the related standard deviations.

Note that a dose-response signal is detected (ie the primary objective is met) as long as either of the dose-response signals for the two regimens is detected. Therefore, the overall study power is at least the maximum of the powers between two regimens for each scenario considered.

Table 3-1 Power for detecting a significant dose response signal*

Dose regimen	Effect size for best dose	SD	Average power**	Minimum power†
Qd	5 %	5.5 %	99.99 %	99.98 %
	5 %	6.5 %	99.71 %	99.57 %
	6 %	5.5 %	99.99 %	99.99 %
	6 %	6.5 %	99.99 %	99.98 %
Bid	5 %	5.5 %	99.16 %	95.84 %
	5 %	6.5 %	96.50 %	86.79 %
	6 %	5.5 %	99.90 %	99.43 %
	6 %	6.5 %	99.28 %	96.36 %

Dose regimen	Effect size for best dose	SD	Average power**	Minimum power†
--------------	---------------------------	----	-----------------	----------------

* Assumes 432 subjects in LIK066 and placebo arms with effective sample size of 367 subjects due to an effect of missing data equivalent to 15 % fewer subjects. Calculations were performed using the DoseFinding package in R.

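### The powers in protocol Table 9-2 and SAP Table 3-1 do not follow from their stated inputs: they match 432 analysed subjects, not 367, with bid effects scaled to a dose no bid arm receives

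*Protocol*

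**What the plan says.** Protocol Section 9.8 plans 432 randomised subjects and allows for missing data: "It was assumed that the effect of losses to follow-up is equivalent to effectively having 15 % fewer subjects than randomized". The Table 9-2 footnote carries that into the powers: "Assumes 432 subjects in LIK066 and placebo arms with effective sample size of 367 subjects due to an effect of missing data". SAP Section 3 prints the same figures in Table 3-1 and likewise describes them as calculated "with effective sample size of 367 subjects due to an effect of missing data equivalent to 15 % fewer subjects".

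The test is set out in protocol Section 9.4.2. There are six candidate shapes for qd and six for bid (Table 9-1), and the threshold "is the common critical value derived from the reference multivariate t-distribution with the" 12 x 12 correlation matrix, obtained "with respect to comparing all candidate models in both dosing regimens to the common placebo group". Section 9.8 adds that the "overall family-wise type I error is controlled at a one-sided significance level of 2.5" %. Candidate shapes are parameterised "with the doses used to define parameters of interest being defined as total daily dose", so the bid arms lie at 5, 10, 50 and 100 mg/day.

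The table gives power by regimen for effects of 5 % and 6 % at the best dose. On the bid shapes the footnote says: "The candidate model #5 in bid regimen has the lowest power".

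**The concern.** The inputs are complete enough to recalculate the table, and the recalculation disagrees with it in two ways.

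- **Sample size.** The stated 367 subjects do not give the printed powers under the specified test; 432 do. A reader would believe the 15 % loss has been absorbed when it apparently has not.
- **Bid effect.** The linear bid model can be the weakest shape, as the footnote says, only if its maximum is placed beyond the highest bid dose. The effect column then does not describe the effect at any bid dose in the trial.

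These are the only power figures in either document. In the bid rows the two departures pull in opposite directions, so the reader cannot tell which bid power applies.

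**Working it through.** **Inputs.** One-sided family-wise alpha 2.5 %; effect 5 % or 6 %; SD 5.5 % or 6.5 % (Section 9.8, Table 9-2). Allocation from Section 9.8: placebo 2 units, each regimen 1:1:1:2, 12 units in total. One unit is 36 subjects at N = 432 and 30.6 at 0.85 x 432 = 367.2. Total daily doses: qd 0, 2.5, 10, 50, 150 mg; bid 0, 5, 10, 50, 100 mg. Shapes from Table 9-1.

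**Method.** For each shape with group means m_i, the optimal contrast is c_i proportional to n_i(m_i - m̄), where m̄ is the n-weighted mean over placebo and that regimen's four doses. The statistic is Σc_i ȳ_i / (S √Σ(c_i²/n_i)). C solves P(max of 12 statistics ≥ C) = 0.025 under no effect, with nine arms, a shared placebo and df = N - 9. Power for a regimen is P(max of its 6 statistics ≥ C) under each shape, then averaged and minimised over the six shapes. Evaluation was by simulation with 1.5 million draws. C is 2.486 at N = 432 and 2.488 at N = 367.

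**Results, average / minimum power (%).**

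| Row (effect/SD) | Printed | 432, bid max over 0-150 | 367, bid max over 0-150 | 367, bid max over 0-100 | 367, best studied bid dose |
|---|---|---|---|---|---|
| bid 5/5.5 | 99.16 / 95.84 | 99.16 / 95.85 | 98.23 / 92.22 | 99.88 / 99.72 | 99.92 / 99.85 |
| bid 5/6.5 | 96.50 / 86.79 | 96.52 / 86.84 | 93.87 / 80.30 | 98.76 / 97.67 | 99.02 / 98.48 |
| bid 6/5.5 | 99.90 / 99.43 | 99.90 / 99.44 | 99.72 / 98.44 | 100.00 / 99.99 | 100.00 / 100.00 |
| bid 6/6.5 | 99.28 / 96.36 | 99.28 / 96.37 | 98.45 / 93.01 | 99.91 / 99.78 | 99.94 / 99.89 |
| qd 5/6.5 | 99.71 / 99.57 | 99.71 / 99.58 | 99.09 / 98.75 | as left | as left |
| Lowest bid model | #5 | #5 | #5 | #6 | #4 |

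The 432-subject column reproduces every printed entry to within 0.05 points (up to 0.08 in repeat runs) or at the 99.99 % cap. At 367 with the same scaling the largest miss is 86.79 - 80.30 = 6.49 points. With the bid maximum inside 0-100 mg/day it is 97.67 - 86.79 = 10.88 points the other way. At 432 with 0-100 scaling, bid 5/6.5 is about 99.6 / 99.1, which also fails to match.

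**Sample size taken alone.** The qd rows do not depend on bid scaling. For qd 5/6.5 the printed minimum leaves a miss rate of 100 - 99.57 = 0.43 %, while 367 subjects give 100 - 98.75 = 1.25 %. Varying N with 0-150 scaling gives largest deviations of 6.6 points at 367, 3.0 at 400, 0.24 at 430, 0.07 at 432 and 0.53 at 440 (400,000 draws).

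**Hand check on the linear bid contrast alone.** Its noncentrality is (slope/SD) √(u × [Σw d² - (Σw d)²/Σw]), with weights w = 2, 1, 1, 1, 2 and u the unit size. The bracket is 22,625 - 265²/7 = 12,592.9. For effect 5 %, SD 6.5 %:

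- 432, slope 5/150: (5/150) √(36 × 12,592.9)/6.5 = 3.45; normal-approximation power Φ(3.45 - 2.49) ≈ 83 %.
- 367, slope 5/150: (5/150) √(30.6 × 12,592.9)/6.5 = 3.18; Φ(3.18 - 2.49) ≈ 76 %.
- 367, slope 5/100: 4.78; Φ(4.78 - 2.49) ≈ 99 %.

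Taking the maximum over six contrasts lifts the first two to the simulated 86.8 % and 80.3 %.

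**What a 5 % bid row then means.** Scaled over 0-150 mg/day, the effect at the best studied bid dose for models #1 to #6 is 4.92, 4.44, 3.96, 4.62, 3.33 and 4.55 %. For the linear model this is 5 x 100/150 = 3.33. For the quadratic, d - 0.007d² peaks at 1/0.014 = 71.4 mg/day with value 35.71; at 50 mg/day it is 32.5, so 5 x 32.5/35.71 = 4.55.

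**The case against.** The strongest reply is that nothing turns on this. Section 9.8 counts a signal in either regimen as success. At 367 subjects qd alone has at least about 98.7 % power in every row, and the 80 % figure is one shape in one row for one regimen. Section 9.8 also expects multiple imputation to recover some information, so 367 is a cautious floor. The SAP's document history already cites Week 24 results, so a correction now serves the record. All of that stands, and it limits the consequence. It does not make the table agree with its footnote.

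The cause is also inferred. Two other settings come close at 367, both still with 0-150 mg/day scaling:

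- **Separate six-contrast critical values per regimen** (about 2.21 qd and 2.24 bid): within 0.60 points, but all 14 uncapped entries fall below print, and Section 9.4.2 specifies one common value.
- **A joint one-sided 5 % test:** within about 0.7 points, but Section 9.8 specifies 2.5 %.

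Both fit less closely than 432, and under either the table would still depart from the specified test.

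Finally, Figure 9-1 is not visible in the text available. If its bid panel runs to 150 mg/day, the scaling range is disclosed there. That would answer the missing range, but not the 367 mismatch or the best-dose label. The 4.55 % for model #6 is no evidence for the 150 mg/day range either: its peak at 71.4 mg/day lies inside both ranges and is simply not a studied dose. Models #1 to #5 carry that part.

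**Conclusion.** The concern holds. Under the documents' own test and allocation, 367 subjects do not produce Table 9-2 or Table 3-1 with any of the three bid scalings examined. That the table does not follow from its stated inputs is firm. That the cause is use of 432 subjects is the best-fitting explanation, but remains an inference without the power code.

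At 367 with 0-150 mg/day scaling, printed bid minima are too high by between 99.43 - 98.44 = 0.99 and 6.49 points. If the effect is meant to apply within the bid range, the printed bid powers are too low and the footnote names the wrong model. The qd entries shift by less than one point.

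This is a reporting error. The sample size, the test and the decision rule are not threatened. The figures assume df = N - 9, missing data acting as a uniform 15 % loss across arms, and the SDs as printed.

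**What to change.** Rerun the power calculation at 367 effective subjects (61.2 on placebo; 30.6, 30.6, 30.6 and 61.2 per regimen) with the common 12-contrast critical value, report that value (about 2.49), and replace Table 9-2 and Table 3-1. State the dose range over which bid effects are scaled, choosing one of:

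- **(a) Keep 0-150 mg/day.** Relabel the bid effect column as the maximum over that range, and give the linear-model effect implied at 50 mg bid: 3.33 % in the 5 % rows, and 6 x 100/150 = 4.00 % in the 6 % rows. The footnote naming model #5 stays correct.
- **(b) Scale within the bid range.** Name the rule and change the footnote to model #6 (curve maximum over 0-100 mg/day) or model #4 (best studied dose).

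The cost is one rerun and one replacement table in each document. Under (a) some figures become less favourable, with a minimum bid power of about 80 % in one row. The sample size does not change.
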